#### 4.1.6 Treatment Cohorts and Treatment Schema

In cohorts 1 and 2, IACS-010759 was administered orally daily on a continual 21-day schedule (1 cycle = 21 days of daily dosing), with the exception that the first cycle for each subject contains a 7-day single dose lead-in (first cycle = 28 days). Starting on day 8 of cycle 1 for subjects enrolled in cohorts 1 and 2, dosing is on a 21 day schedule until confirmed PD, initiation of alternative cancer therapy, unacceptable toxicity, or other reasons to discontinue treatment prematurely occur as defined in Section 4.1.9.

Based on PK modeling of data from cohorts 1 and 2, the dose regimen for cohort 3 and subsequent cohorts will change to include an induction phase with daily dosing, followed by a maintenance phase at a dose sufficient to maintain the steady state levels achieved during the induction phase. In these cohorts, IACS-010759 will be administered orally daily (up to 7 days) during the induction phase(Cycle 1, Days 1-7). Starting on day 8 of cycle 1 for all cohorts, maintenance dosing will be administered on a 21-day schedule until confirmed PD, initiation of alternative cancer therapy, unacceptable toxicity, or other reasons to discontinue treatment prematurely occur as defined in Section 4.1.9.

The planned dose levels are given in Table 1 and 2, below:

Table 1: Dosing schema for Cohorts 1 and 2

PHASE	COHORT	NO OF SUBJECTS	IACS-010759 DOSE LEVEL *
Dose-	Cohort 1	3-6	0.5 mg
escalation	Cohort 2	3-6	1 mg

\*Intermediate doses of IACS-010759, not to exceed 8 mg, not listed above may also be pursued with SMC approval, depending on the safety, PK and PD data observed.

Table 2: Revised dosing schema for Cohorts 3-6 (Dose-Escalation) and Cohort 7 (Dose Expansion)

PHASE	COHORT	NO OF SUBJECTS	INDUCTION DOSE* (FREQUENCY#)	MAINTENANCE DOSE* (FREQUENCY#)
	Cohort 3	3-6	2 mg (daily, Cycle 1 Day 1-7)	0.5 mg (once per week)
Dose-	Cohort 4**	3-6	2.5 mg (daily, Cycle 1 Day 1-7)	1.0 mg (three times per week)
escalation	Cohort 5	3-6	2.5 mg (daily, Cycle 1 Day 1-5)	1.5 mg (three times per week)
	Cohort 6	3-6	3 mg (daily, Cycle 1 Day 1-5)	2 mg (three times per week)
Expansion	Cohort 7	12	RP2D	RP2D

\*Intermediate induction or maintenance doses of IACS-010759 may be pursued with SMC approval, not to exceed 6 mg, and

# alternative duration of induction doses or other maintenance schedules not listed above may also be pursued with SMC approval depending on the safety, PK and PD data observed.

\*\*Following their review of Cohort 3, the SMC recommended implementation of the following dose schedule for

subjects who enroll in Cohort 4 of the study:

Induction dose: 2.5 mg, administered daily, Cycle 1 Day 1 through Day 7

Maintenance dose: 1 mg, administered 3x/week (for a total weekly dose of 3 mg) with the first maintenance dose starting on Cycle 1 Day 8

#### 4.1.7 Dose-escalation

A standard 3+3 dose-escalation design will be used to determine MTD. The potential dose schedule is shown in section 4.1.6. In the first cohort, as a safety precaution, each new subject began treatment only after the safety analysis for DLTs and evaluation of PK data during the first cycle (28 days) was completed for the previous subject. In subsequent cohorts of the dose-escalation phase, new subjects will be entered and treated only after the previous subject has been treated with IACS-010759 for up to 7 days (e.g., has completed the induction phase) and DLT safety analysis for each subject will be performed after completion of cycle 1. PK data will be monitored for each subject and evaluated for each cohort during the study and plasma levels will be considered when making dose escalation decisions.

The following dose-escalation rules will be applied:

- If 0 out of the 3 subjects have a DLT, the next cohort may be started.
- If 1 out of the 3 subjects has a DLT, an additional 3 subjects will be enrolled in the same cohort. If none of these 3 additional subjects have a DLT after being observed for 28 days (i.e., cycle 1), the next dose escalation cohort may be started.
- If 2 or more out of 6 subjects in Cohort 1 develop a DLT, enrollment will cease immediately and the study will be halted. No MTD can be determined.
- If 2 or more out of 6 subjects in the following Cohorts (2-6) develop a DLT, enrollment into the cohort will cease, and the prior cohort's dose level will be deemed as MTD level. All subjects from the non-tolerated cohort will be de-escalated to the prior cohort's dose level.
  - If at least 2 of 3 or 2 of up to 6 patients experience a DLT at a given dose, then the MTD has been exceeded (stopping dose). Once the MTD has been exceeded, treat another 3 patients at the previous dose if there were only 3 patients treated at that dose.

During dose escalation, if necessary, cohorts may be expanded in the absence of a DLT, to a total of up to 6 subjects to further explore safety, PK and PD activity of IACS-010759 at each dose level with the approval of the SMC. Such an expansion may occur concurrently with dose escalation to the next dose level. A predetermined allocation to cohorts that minimizes selection bias will be used when enrolling into two open cohorts simultaneously. Allocation to simultaneously open cohorts will be performed in an alternating random manner, based on entry into the study. During dose escalation, intermediate (including induction or maintenance) doses and alternative duration of induction doses or other maintenance schedules of IACS-010759, not to exceed 6 mg, may also be pursued with SMC approval, depending on the safety, PK and PD data observed.

The dose escalation phase of the study will be paused after the dose at which the mean steady state plasma levels, measured as pre-dose concentrations on Day 28 for cohorts 1 and 2 and as pre-dose concentrations on Day 8 (e.g. the end of the induction phase) for cohorts 3 onwards, reach levels of  $\geq$ 20 nM (11 ng/mL). A full review of the safety, PK and efficacy data from that

cohort will be performed and escalation may be continued if the MTD has not been reached, and the Sponsor obtains agreement with FDA to continue dose escalation.

The dose escalation phase of the study will stop after the dose for which the mean Cmax on Day 28 for cohorts 1-2 or Day 7 for cohorts 3 and onwards is  $\geq$ 100 nM, or after the dose for which the mean steady state concentration for the cohort, as measured on the last day of any 21 day Cycle, is  $\geq$ 100 nM, whichever dose is lower.

To assess toxicities that may occur beyond cycle 1, cohorts of up to 6 subjects will be assessed following completion of 4 cycles of study drug. If two or more subjects in the cohort did not receive at least 80% of the planned dose due to adverse events, dose escalation will be paused and an evaluation will be performed.

Once the MTD has been established or the dose-escalation completed without identifying a MTD, the RP2D will be defined based on an assessment the safety, pharmacokinetic (PK), pharmacodynamic (PD), biomarker, and response data.

At the discretion of the sponsor, dose-escalation may be stopped before an MTD is reached. In this case, the RP2D may be chosen based on an assessment of the safety, PK, PD, biomarker, and response data evaluable up to that time. An MTD does not have to be reached to expand a dose cohort if the available data demonstrate that a lower dose level may provide antitumor activity while minimizing potential risk. Upon completion of the dose-escalation, the cohort with either the highest dose level shown to be well tolerated or the RP2D will be expanded to a total of 6 subjects (if not already expanded to 6 subjects due to either observation of a DLT or to further explore safety, PK and PD activity of IACS-010759 at that dose level).

Late onset DLTs that could not be taken into consideration prior to scheduled dose escalations will be ad-hoc evaluated on a case-by-case basis, and may lead to enrollment of additional subjects in specific cohorts or to revision of the previously determined MTD.

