- Cmax on Day 28 from pivotal toxicity studies was 61.3 ng/mL in rats and 99.3 ng/mL in monkeys at doses of 1 mg/kg/day and 1.5 mg/kg/day, respectively. These Cmax values, which were observed at doses that were well tolerated for 28 days in each species, were notably higher than steady state trough plasma levels of 5.6 11.3 ng/mL at which efficacy was consistently observed in nonclinical xenograft models of human tumor cells. Because the human peak:trough plasma levels with daily oral dosing are projected to be <2-fold based on projected human clearance and on the preliminary data from cohorts 1 and 2 of the

present study, this represents a significant exposure multiple above the projected human exposure required for efficacy.

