Limited PK data from subjects in cohorts 1 and 2 showed unexpected levels of accumulation of IACS-010759 throughout the dosing period, consistent with a model in which the clearance of IACS-010759 decreases exponentially with time, leading to an increasingly long terminal  $T_{1/2}$  and accumulation upon multiple dosing. A mathematical model and simulation has been developed based on data from the subjects treated with IACS-010759 to date that predicts the observed human PK. Based on this model, a modified dosing regimen is being implemented for the dose escalation phase with cohorts 3-6 and for the dose expansion phase with cohort 7, consisting of an induction phase in which IACS-010759 is administered daily for up to 7 days, followed by a maintenance phase in which a lower dose is administered weekly to maintain steady state plasma levels (or as otherwise specified by the SMC based on safety, PK and PD data observed).

Page 17 of 59

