<sup>M In addition to the time points indicated in the Table, additional draws from peripheral blood for PK analysis may be obtained at the discretion of the Investigator.

<sup>N Baseline dilated eye exam with fundus photos, including distance acuity (visual acuity charts using refraction-based visual acuity measurement), ophthalmoscopy and slit lamp exam, may be performed up to 14 days prior to study drug administration.

<sup>o Baseline neurology review and exam to be performed by consultant neurologist up to 14 days prior to study drug administration. The baseline neurology exam may include, but is not limited to, gait and station, cerebellar functions (coordination), upper and lower extremity reflexes, upper and lower muscle strength and sensation.

<sup>P The dose regimen for the induction and maintenance doses are provided in Table 2.

<sup>1 collected pre-dose (same calendar day of dosing) and 4 hours +/- 30 minutes post study drug administration

<sup>2 collected pre-dose (same calendar day of dosing) and 2, 4, 6, 8 hours (+/- 30 mins) post study drug administration. Note: vitals may be collected (+/- 60 mins) post study drug administration.

<sup>3 collected pre-dose (same calendar day of dosing)

<sup>4 collected pre-dose (same calendar day of dosing) and 2, 4, 6, 8 hours (+/- 30 mins) and 24 hours (+/- 2 hours) post study drug administration. Note: vitals may be collected (+/- 60 mins) post study drug administration.

- \* Treatment will be administered as an inpatient for 24 hours on Day 5 of Cycle 1.
- + Subjects enrolled in the Food Effect group will consume a high fat meal within 30 minutes prior to study drug administration on Day 1 blood sample collection. § Study drug will be administered without food, at least 1 hour before and at least 2 hours after eating, with the exception of Day 1 of Cycle 1 for subjects enrolled in the Food Effect group. Induction or maintenance doses and alternative duration of induction doses or other maintenance schedules of IACS-010759, not to exceed 6 mg, may be pursued depending on the safety and PK/PD data observed.
- ¥ Bone marrow aspirate/biopsy will be performed as clinically indicated, at least once every 3 cycles.

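### The PK stop and pause rules in Section 4.1.7 still use Day 7 and Day 8, although induction ends on Day 5 in cohorts 5 and 6

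*Combined protocol and SAP*

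**What the plan says.** Section 4.1.7 (Dose-escalation) has two plasma-level rules.

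- **Pause at a mean of 20 nM or more.** It is read from "pre-dose concentrations on Day 8 (e.g. the end of the induction phase) for cohorts 3 onwards". Escalation may resume after a full review of safety, PK and efficacy, provided the MTD has not been reached and FDA agrees.
- **Stop at a mean of 100 nM or more.** One limb uses "the mean Cmax on Day 28 for cohorts 1-2 or Day 7 for cohorts 3 and onwards". The other uses the mean steady-state concentration "as measured on the last day of any 21 day Cycle". Whichever dose is lower applies, and no provision is made for lifting the stop.

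Table 2 in Section 4.1.6 gives cohorts 3 and 4 seven days of induction. Cohort 5 receives "2.5 mg (daily, Cycle 1 Day 1-5") and cohort 6 "3 mg (daily, Cycle 1 Day 1-5"). Maintenance starts on Day 8 in all of them.

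In the Section 4.2 flowchart for cohorts 5-7, the Cycle 1 visits are Days 1, 2, 4, 5, 8, 12 and later. The PK profile that cohorts 3-4 have on Day 7 is taken on Day 5: pre-dose, then "2, 4, 6, 8 hours (+/- 30 mins) and 24 hours (+/- 2 hours) post study drug administration" (footnote 4 of that flowchart).

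**The concern.** Both rules cover every cohort from 3 onward without exception, yet the days they name fit only a seven-day induction. In cohorts 5 and 6 the Day 7 Cmax has no dose to produce it and no scheduled sample to measure it. The Day 8 pre-dose sample exists, but it is not the end of induction as 4.1.7 describes it, because no drug is given on Days 6 and 7.

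The planned decision at stake is cohort 5 to cohort 6, plus any step beyond cohort 6 that the SMC approves within the 6 mg cap. A Cmax that should stop escalation would only pause it, unless the last-day-of-cycle mean also reached 100 nM. The pause itself would use a later and lower reading than in cohorts 3-4, so the same 20 nM limit would not mean the same exposure across cohorts. Cohort 7 is expansion and is not governed by these rules.

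**Working it through.** **Inputs.** Doses and induction days are from Table 2, sampling days from Section 4.2, and thresholds from 4.1.7. The free-base molecular weight is 562.564 g/mol (Section 2.2.3). Animal half-lives are 42-57 h, and human peak:trough with daily dosing is projected below 2 (both Section 2.2.2). No human half-life is given. Section 3.1 reports data consistent with a model in which "the clearance of IACS-010759 decreases exponentially with time", so I assume 100, 200 and 400 h and show the animal values for comparison. The model is one-compartment with constant half-life *t* and immediate absorption.

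**The plan's own figure.** 20 nM × 562.564 / 1000 = 11.25 ng/mL, which matches the stated 11 ng/mL.

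**Timing of Day 8 pre-dose after the last induction dose.** Cohorts 3-4: (8 − 7) × 24 = 24 h. Cohorts 5-6: (8 − 5) × 24 = 72 h.

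**Effect on the pause.** The Day 8 level divided by the 24 h post-Day-5 level is 2^(−48/*t*). The 24 h level that would read as 20 nM on Day 8 is 20 divided by that ratio.

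| *t* (h) | Ratio | 24 h level reading as 20 nM |
|---|---|---|
| 42 (animal) | 0.453 | 44.2 nM |
| 57 (animal) | 0.558 | 35.9 nM |
| 100 | 0.717 | 27.9 nM |
| 200 | 0.847 | 23.6 nM |
| 400 | 0.920 | 21.7 nM |

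**Exposure relative to cohort 4.** The level 24 h after the last of *n* daily doses *D* is proportional to *D* × Σ 2^(−24k/*t*), k = 1 to *n*. Cohort 4 is 2.5 mg × 7.

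| Regimen | 100 h | 200 h | 400 h |
|---|---|---|---|
| Cohort 5 (2.5 mg × 5), 24 h level | 0.821 | 0.771 | 0.743 |
| Cohort 6 (3 mg × 5), 24 h level | 0.985 | 0.925 | 0.892 |
| Cohort 6, Day 8 reading | 0.706 | 0.783 | 0.821 |
| 6 mg × 5 (SMC cap), 24 h level | 1.97 | 1.85 | 1.78 |

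The third row is the second multiplied by the ratio above. Cohort 6 equals cohort 4 at *t* = 88 h. At 42 h the 24 h level is 0.919 of cohort 4's in cohort 5 and 1.103 in cohort 6.

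**Does the pause back up the missing Cmax limb?** Section 2.2.2 states that "human peak:trough plasma levels with daily oral dosing are projected to be <2-fold". A mean Cmax of 100 nM then implies a 24 h level above 100 / 2 = 50 nM. Multiplying by the ratio puts Day 8 above about 36, 42 and 46 nM at 100, 200 and 400 h, and above 22.6 nM at 42 h. All exceed 20 nM, so the pause fires in every case, but the Cmax stop does not.

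**The case against.** The case against accepts that the Day 7 Cmax limb cannot be read in cohorts 5-6. Its other points are these.

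- **The section was revised.** The amendment log shows that Amendment 10 changed 4.1.7 to say induction lasts up to seven days. That is correct: only the PK trigger days were left behind.
- **The pause rule can be executed.** The Day 8 sample is scheduled with no visit window, 24 h is nowhere stated as the intended interval, and the end-of-induction label is introduced only as an example. Day 8 may have been kept on purpose. The 24 h standard is indeed an inference from cohorts 3-4. But the label is untrue for cohorts 5-6, and the log entry for Amendment 5 ties Days 7 and 8 to the end of induction. No text says a 72 h reading was intended.
- **Planned exposures are low.** Induction totals are 17.5 mg in cohort 4 (2.5 × 7), 12.5 mg in cohort 5 (2.5 × 5) and 15 mg in cohort 6 (3 × 5). Cohort 5 is unlikely to cross a limit that cohort 4 did not. The 6 mg case needs SMC approval and is not planned. This stands, and it limits the urgency.
- **Other safeguards exist.** The last-day-of-cycle limb still works, extra PK draws are allowed, and the SMC considers plasma levels in escalation decisions. This also stands, but a mandatory stop should not depend on discretion.
- **The half-life is assumed.** The direction holds under any decay. The size does not: at 400 h the shift is only 8%.

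**Conclusion.** The concern holds. In cohorts 5 and 6 one limb of the mandatory 100 nM stop cannot be evaluated from scheduled samples, and the 20 nM pause is read 48 h later than in cohorts 3-4. Both follow from the current text and need no model.

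The size rests on an assumed constant half-life of 100-400 h: a Day 8 reading 8-28% low, with 24 h means up to about 22-28 nM escaping the pause. The animal half-lives would make it 44-55% low, probably an upper bound given the slowing clearance. The practical risk is small for cohort 5 and modest for cohort 6, whose 24 h level is 89-98% of cohort 4's but whose Day 8 reading is only 71-82%. It grows if the SMC approves higher five-day inductions. This should be fixed, but it does not leave escalation without PK limits.

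**What to change.** In Section 4.1.7, tie both rules to the last day of induction. The stop then uses mean Cmax on that day, and the pause uses the mean concentration 24 h after that day's dose. This gives Day 5 Cmax and the 24 h post-Day-5 level in cohorts 5-6, and leaves Day 7 and Day 8 pre-dose in cohorts 3-4. It would also cover other induction lengths the SMC may approve, provided the profile is sampled on the last induction day. Leave the last-day-of-cycle limb as it is.

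The cost is wording in 4.1.7 only, since the Day 5 serial samples and the 24 h sample are already in the flowchart. No threshold, planned dose or visit changes. The one substantive effect is that the pause becomes somewhat stricter in cohorts 5-6 than under the present text, which restores the basis used in cohorts 3-4.

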#### 4.1.8 Expansion Phase

Subjects in the expansion phase will be treated at the RP2D level determined in the dose-escalation phase.

The primary objective of the expansion phase is to determine safety of IACS-010759.

Additionally, as part of the expansion phase, the effect of a high fat meal on the PK of IACS-010759 (Food Effect) will be evaluated in a total of 6 subjects (Food Effect cohort), as described in Section 7.1. After the first 6 subjects have been enrolled in the expansion cohort, the next 6 subjects will be enrolled in the Food Effect cohort.

To evaluate safety, the method of Thall, Simon and Estey [20] will be used for monitoring DLTs occurring in the first cycle. The probability of DLT is denoted by  $P_T$ . We assume  $P_T \sim$  beta (0.4, 1.6). Our stopping rule is given by the following probability statement:  $Pr(P_T > 0.20 \mid data) > 0.80$ .

That is, if at any time during the study we determine that there is more than 80% chance that the unacceptable toxicity rate is more than 20% during the expansion phase, then the enrollment will be stopped. Subjects will be monitored by a cohort size of 6 during the expansion phase according to the following stopping boundaries for DLTs, starting from the 12th

subject. The monitoring rule for DLTs, based on these assumptions and monitoring conditions is found in Table 3. For example, accrual in the expansion phase will cease if 4 or more subjects experience DLTs among the first 12 subjects. The operating characteristics are summarized in Table 4. The design software Multc Lean Desktop (version 2.1) developed by the Department of Biostatistics at M. D. Anderson Cancer Center was used to generate the toxicity stopping boundaries and the operating characteristics tables.

Table 3 Stopping boundaries for DLT monitoring

# Subjects evaluated	12	18
# Subjects with DLTs	4-12	6-18

Table 4 Operating characteristics of toxicity monitoring

True DLT Rate	Early Stopping Probability	Average Sample Size
0.10	0.0256	17.8
0.15	0.0922	17.4
0.20	0.2054	16.8
0.25	0.3512	15.9
0.30	0.5075	15.0

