#### 4.1.5 Sample Size Considerations

The dose-escalation phase of the study will enroll 3-6 subjects in each cohort, based on a 3+3 dose-escalation design to assess the MTD level. A maximum of 36 subjects will enroll in the dose-escalation phase.

A maximum of 18 subjects will enroll in the expansion phase (12 additional subjects and the 6 subjects from the dose-escalation phase at the cohort of the highest dose level shown to be well tolerated or the RP2D). The expansion phase sample size of 18 subjects is not based on a formal sample size calculation. Rather, 18 subjects are deemed to be sufficient for the assessment of safety and tolerability as the primary objective and the exploration of clinical anti-tumor activity and other secondary and exploratory endpoints.

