#### 4.1.10 DLT, MTD and RP2D definitions

The MTD is defined as the highest dose studied for which the observed incidence of DLT is less than 33%. Frequencies of toxicities will be tabulated according to the NCI Common Toxicity Criteria version 4.03.

The RP2D will be determined based on the safety data and all available correlative data from the escalation phase by the Safety Monitoring Committee.

Dose-limiting toxicity (DLT) is defined as a clinically significant non-hematologic adverse event or abnormal laboratory value assessed as unrelated to disease progression, intercurrent illness, or concomitant medications and is possibly, probably or definitely related to the study drug and occurring during the first cycle (21 days) on study that meets any of the following criteria:

- All Grade 4 non-hematologic toxicities of any duration
- All grade 3 non-hematologic toxicities. Exceptions are as follow:
  - Grade 3 nausea, vomiting and diarrhea that does not require hospitalization or TPN support and can be managed with supportive care to ≤ grade 2 within 48 hours.
  - Grade 3 electrolyte abnormalities that are corrected to ≤ grade 2 within 24 hours

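### The expansion stopping rule is worded as continuous, but only the look at 12 subjects can stop accrual, and Table 4 counts six pre-screened escalation subjects as new

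*Combined protocol and SAP*

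**What the plan says.** Section 4.1.8 (Expansion Phase) gives the DLT probability a Beta(0.4, 1.6) prior and stops enrollment when Pr(P_T > 0.20 | data) > 0.80. It explains the rule in words as acting "if at any time during the study we determine that there is more than 80% chance" that the limit is exceeded.

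It then narrows the schedule: "Subjects will be monitored by a cohort size of 6 during the expansion phase", with the "following stopping boundaries for DLTs, starting from the 12th" subject. Table 3 gives two boundaries, 4 or more DLTs at 12 subjects and 6 or more at 18. The text illustrates the first: "accrual in the expansion phase will cease if 4 or more subjects experience DLTs among the first 12 subjects". Table 4 lists early stopping probabilities and average sample sizes for true DLT rates of 0.10 to 0.30.

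Section 4.1.5 (Sample Size Considerations) fixes the denominator: "A maximum of 18 subjects will enroll in the expansion phase (12 additional subjects and the 6 subjects from the dose-escalation phase" at the selected dose). Section 4.1.7 treats a dose as too toxic "If at least 2 of 3 or 2 of up to 6 patients experience a DLT at a given dose", and section 4.1.10 defines the MTD as the "highest dose studied for which the observed incidence of DLT is less than 33" percent. Under section 6.1 the first six new subjects are followed by six in the Food Effect group.

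**The concern.** The verbal rule and the table cannot both govern. Suppose the six carried-over subjects had one DLT and the first two new subjects each have one. That is 3 of 8. The probability statement is met, so the sentence says stop, while Table 3 has no boundary until 12. After subject 12 the conflict is wider, because the only remaining boundary falls when everyone has been enrolled.

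A second question is what Table 4 describes. Its figures are those of 12 fresh subjects, but the first six have already passed the escalation rules. A reader who uses Table 4 to judge how likely the rule is to stop a toxic dose may be reading the wrong probability.

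Safety is the stated primary objective of the expansion phase. Both points bear on when accrual stops and on how the rule's performance is described.

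**Working it through.** **Inputs.** Prior Beta(0.4, 1.6), limit 0.20, cutoff 0.80, Tables 3 and 4 (section 4.1.8); maximum 18 = 12 new + 6 carried over (4.1.5); at most 1 DLT in the carried-over six (4.1.7; also 4.1.10, since 1/6 = 16.7% is below 33% and 2/6 = 33.3% is not).

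**1. Table 3.** With x DLTs in n subjects the posterior is Beta(0.4 + x, 1.6 + n − x).
- n = 12: x = 4 gives 0.821, x = 3 gives 0.608, so the boundary is 4.
- n = 18: x = 6 gives 0.883, x = 5 gives 0.747, so the boundary is 6.

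Both printed boundaries are correct.

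**2. Table 4.** One look at 12 stops with probability P(Bin(12, p) ≥ 4), and the average sample size is 18 − 6 × that probability.

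| True rate | Printed | One look at 12 | Looks at 12 and 18 |
|---|---|---|---|
| 0.10 | 0.0256 | 0.0256 | 0.0273 |
| 0.15 | 0.0922 | 0.0922 | 0.1022 |
| 0.20 | 0.2054 | 0.2054 | 0.2339 |
| 0.25 | 0.3512 | 0.3512 | 0.4043 |
| 0.30 | 0.5075 | 0.5075 | 0.5814 |

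At 0.30 the average sample size is 18 − 6 × 0.5075 = 14.96, printed as 15.0. Table 4 is therefore the single look at 12, with 18 not counted as a stop.

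**3. Counts that meet the criterion with no operative boundary.** 3 of 8: 0.825. 4 of 10: 0.895. 5 of 14: 0.886. 5 of 16: 0.822. All are reachable with one DLT carried over. The full set of implied boundaries from n = 8 is 3 at 8, 4 at 9–12, 5 at 13–16 and 6 at 17.

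**4. Table 4's single look, given 0 or 1 DLT in the first six.** With 0 carried over, four of the next six must have a DLT; with 1 carried over, three must. Weights are proportional to (1 − p)^6 and 6p(1 − p)^5.
- p = 0.20: weights 0.2621 and 0.3932, that is 0.40 and 0.60. Stopping = 0.40 × 0.0170 + 0.60 × 0.0989 = 0.066 (printed 0.2054).
- p = 0.30: weights 0.1176 and 0.3025, that is 0.28 and 0.72. Stopping = 0.28 × 0.0705 + 0.72 × 0.2557 = 0.204 (printed 0.5075).

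**5. The verbal rule applied after each new subject.** Exact recursion over subjects 7–17 on the same condition, with each outcome known before the next subject is dosed.

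| True rate | Stop, look at 12 only | Stop, each subject 7–17 | New subjects dosed |
|---|---|---|---|
| 0.20 | 0.066 | 0.116 | 11.6 vs 11.3 |
| 0.30 | 0.204 | 0.341 | 10.8 vs 10.0 |
| 0.40 | 0.400 | 0.608 | 9.6 vs 8.2 |

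**6. Where the gain arises.** Adding only looks at 7–11 to the look at 12 moves stopping from 0.204 to 0.219 at 0.30, and from 0.400 to 0.417 at 0.40. Adding only looks at 13–17 gives 0.330 and 0.600. Nearly all of the change in stopping probability comes after subject 12; the earlier looks mainly bring a stop forward.

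**The case against.** The schedule is not hidden. The sentence after the verbal rule gives cohorts of six from the 12th subject, and Table 4 quantifies that schedule correctly. A reader might infer that Tables 3 and 4 are miscalculated, or that the plan fails to deliver the protection it prints. Neither is supported: both tables reproduce, and Table 4 is right for a single look at 12 fresh subjects. What is missing is only the continuous protection that the wording implies. Looking by cohort is a legitimate choice.

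A reader might also infer that the absence of a boundary before 12 is the main hole. It is not. With at most 1 DLT carried over, a look at 6 (which needs 3) could never stop and 3 of 7 cannot occur. The look at 12 comes after only six new subjects.

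The saving in subjects is modest and depends on timing. The DLT window is 21 days, and the up-to-7-day stagger in section 4.1.7 is stated only for dose escalation. If two further subjects are dosed while an outcome is pending, the figures at a true rate of 0.40 become 10.4 versus 9.4 new subjects. Subjects 13–18 are the Food Effect group, fed on day 1 and possibly at a lower dose (section 6.1), so pooling them for subject-by-subject looks needs a decision.

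Finally, the Safety Monitoring Committee may recommend termination at any time (section 4.1.14.1), so subjects after the 12th are not without oversight. That power is discretionary and has no threshold, so it does not resolve which version of the prespecified rule applies.

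What stands is the conflict between sentence and table, the single effective look, and the mismatch between Table 4 and the composition of the first 12.

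**Conclusion.** The point holds in a limited form. Section 4.1.8 gives two rules that lead to different actions at reachable counts. As tabulated, one look can stop accrual, and none can do so at subjects 13–17.

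Table 4 is arithmetically correct but does not describe this design once the six carried-over subjects are recognised. At a true rate of 0.30 its stopping probability is about 0.20 (0.07 if none of the six had a DLT, 0.26 if one did), not 0.51. The same condition lowers the chance of stopping at exactly the 20% limit, to 0.066 from 0.2054, so the printed table overstates stopping in both directions.

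These figures assume exactly six evaluable carried-over subjects with 0 or 1 DLT, binomial weights and a common DLT rate. The comparison of schedules also assumes immediate outcomes. The documents do not show that the one-look design is unsafe or that continuous looks are required. They show that the plan must say which it means and report matching operating characteristics.

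**What to change.** Reconcile the sentence with Table 3 in one of two ways:

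- **(a) Keep the continuous wording.** Extend Table 3 to the boundaries the probability statement implies: 3 at n = 8, 4 at n = 9–12, 5 at n = 13–16, 6 at n = 17. Apply them as DLT outcomes become known, and label n = 18 as descriptive. If every subject is checked in turn, the entries at 9, 13 and 17 cannot be the first to trigger; they matter when several outcomes arrive together.
- **(b) Keep the cohort schedule.** Delete the at-any-time wording, state that the rule has one effective look, at 12, and label n = 18 as descriptive.

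In either case, re-run Table 4 for the chosen schedule conditional on 0 or 1 DLT in the six carried-over subjects. State how those six and the Food Effect subjects are counted, and what happens to enrollment while a DLT window is open.

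The cost is a text edit and a re-run of the operating characteristics. Option (a) also needs more frequent DLT checks and raises stopping at a true rate of 0.20 from 0.066 to 0.116. Option (b) adds no checks but leaves subjects 13–17 to the committee's judgement, which the plan should then say.
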